APPENDIX 3: SUBSTUDY ADDENDUM A**Background and Objectives:**

Antibiotic medicines are often used to fight infectious diseases in humans and prevent bacterial infection. The implementation of antibiotics into medical practice has had an immeasurable positive impact on world health since their discovery in the early 20th century. However, despite the strengths of antibiotic use in medicine, numerous negative aspects have become more apparent in the last 20-30 years. Specifically, antibiotic abuse, which has resulted in the rise of many antibiotic-resistant bacteria such as MRSA and *Clostridium difficile*. These negative aspects of antibiotic overuse and misuse have resulted in many patients experiencing antibiotic-associated diarrhea (AAD) and increased mortality due to infectious diseases [1].

Oral or intravenous antibiotics can significantly alter the composition of gut microbiota, which increases a patient's likelihood of experiencing AAD. Studies have shown that probiotics have the potential to reduce the rate of AAD in patients taking antibiotics, and as a result, many physicians have begun recommending that patients take probiotics supplements when starting a course of antibiotics [2]. Probiotics, which are live microorganisms that, when administered in adequate amounts, confer a health benefit on the host [3]. Probiotics not only have the potential to reduce a patient's risk of experiencing AAD, but they also play an essential role in maintaining homeostasis and immunologic equilibrium in the gastrointestinal tract [4,5].

Another critical aspect of maintaining gastrointestinal health is the consumption of prebiotics along with probiotics. Prebiotics are defined as a substrate that is selectively utilized by host microorganisms conferring a health benefit [6]. Prebiotics can be acquired through supplements or fiber-rich foods, which are carbohydrate-based; however, not all fiber is considered a prebiotic [6]. To be considered a prebiotic, the substrate must resist gastric acidity, hydrolysis by mammalian enzymes, absorption in the upper gastrointestinal tract, as well as be fermented by the intestinal microflora and selectively stimulate the growth or activity of intestinal bacteria [7].

The mechanism of prebiotics works primarily through their main fermentation pathway, in which the gut generates pyruvate from hexoses in the undigested carbohydrates. Gut bacteria use a range of carbohydrate hydrolysis enzymes to produce hydrogen, methane, carbon dioxide, short-chain fatty acids (SCFAs), and lactate [7]. Specifically, SCFAs are an important product of this mechanism because of their many significant contributions to human health, including nourishing cells that line the gut, enhancing Ca⁺ absorption, relieving constipation and diarrhea, as well as entering the bloodstream and traveling to other organs, and in doing so, act as signals to communicate with the brain and regulate the immune system and inflammation [7].

For this substudy, we aim to use the existing data to explore the effect that a participant's dietary fiber intake has on the occurrence of adverse events related to undergoing a 7-day course of antibiotics. No new data will be collected. Additionally, this substudy seeks to examine if higher consumption of dietary fiber impacts the effect of antibiotic-induced reduction in SCFA concentration as reflected by the levels of acetate in stool samples. The primary hypothesis of this substudy is that a higher intake of dietary fiber will result in participants experiencing fewer adverse events from the antibiotic. Further, this substudy's secondary hypothesis is that a higher intake of dietary fiber will result in less of a reduction in SCFAs by day 7, as well as a quicker return to baseline SCFA.

References:

APPENDIX 4: SUBSTUDY ADDENDUM B**Background and Objectives:**

Antibiotic associated diarrhea (AAD) is one of the most common side effects of antibiotic treatment.[1] AAD typically occurs in 5-35% of patients who take antibiotics.[2] Probiotics are live microorganisms that can have a positive effect on the microflora of the gut by restoring microbial imbalance that may have been caused by antibiotics.[3]

Although male and female digestive systems are similar, anatomical and physiological differences cause variances in digestion, including reactions to food, medications, and metabolism. Women have increased sensitivity throughout the whole digestive tract making them more vulnerable to GI pain, bloating, and nausea.[4] On average, the female colon is 10 centimeters longer than the male colon, contributing to a longer average digestive time of females compared to males.[5] A Mayo Clinic Study found that it took males an average of 33 hours to digest food, while it took females an average of 47 hours.[6] A study examining physician visits for constipation noted that females were more likely to report GI discomfort and seek medical assistance when ill.[7]

Given these differences, it is hypothesized that females in the parent studies (R61/YOBIOTIC and R33/OURBIOTIC phases) would report more GI related adverse events since their biological anatomy tends to predispose them to increased GI discomfort.

We observed more incidences of adverse events reported by females compared to males in the current OURBIOTIC study. For this substudy, we propose analyzing the previously collected data on the adverse events reported by males and females. Since the YOBIOTIC study is so similar to the OURBIOTIC study, we propose studying both cohorts to increase the sample size. Another aim would be to compare any differences between males and females in the Short Chain Fatty Acid data.

References:

1. Bartlett, J. G. (1992). Antibiotic-associated diarrhea. *Clinical Infectious Diseases*, 15(4), 573-581.
2. McFarland, L. V. (2008). Antibiotic-associated diarrhea: epidemiology, trends and treatment.
3. Johnston, B. C., Goldenberg, J. Z., Vandvik, P. O., Sun, X., & Guyatt, G. H. (2011). Probiotics for the prevention of pediatric antibiotic-associated diarrhea. *Cochrane Database of Systematic Reviews*, (11).

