6. STUDY PROCEDURES

6.1 Schedule of Evaluations

All interventions will be completed by day 14 of the trial. At day 30, participants will provide the final sample and be queried for changes in baseline health and other adverse events.

Table 8. Participant Timeline and Sample/Data Collection Schedule (N=60)

Assessment	Pre-screen	Pre Run-In Baseline	30-day Run-In	Post Run-In (0/+2)	1	7 (±2)	14 (±2)	21 (±2)	30 (±2)
Pre-Screening	X								
Informed Consent Form & Process		X							
Inclusion/Exclusion Criteria		X		X					
Enrollment		X ^a							
Baseline Health Status		X							
Demographic Information		X							
Fecal Microbiome Collection ^a	X		X		X	X	X	X	X
Automated Self-Administered 24-Hour (ASA24®) Dietary Assessment Tool (2 days)			X						
Run-in Period (30 days)			→	→					
Post Run-In Health Status				X					
Randomization			X						
Amoxicillin-clavulanate Intervention (7 days)					→	→			
Yogurt Intervention (14 days)					→	→	→		
Follow-up Data Collection						X	X		X
Daily Assessment Diary ^b (14 days)					→	→	→		
Gastrointestinal Symptom Rating Scale (GSRS-IBS)					X	X	X		
SCFA Testing	X					X			X
16S rRNA Gene Sequences				X		X	X	X	X
Adverse Event Reporting		→		→	→	→	→	→	→

^aEnrollment will occur a minimum of 30 days prior to starting the interventions. Participants will provide one stool sample before the run-in period, refrain from antibiotics and probiotics during this period and provide 1 baseline sample after the run-in period.

^bDiary from days 1-14; information on yogurt consumption/dose, sample number, shape and consistency, health, use of interventions, quality of life and adverse events.

X: collected on day; | → : starting from day; → |: through end day

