7.2 Methods and Timing for Assessing, Recording, and Analyzing Safety Parameters

Unanticipated problems will be recorded in the data collection system throughout the study.

Details of all expected and unexpected adverse events reported by participants during follow-up calls, spontaneously, or observed by research personnel must be recorded in the adverse event report forms. Participants will be provided with a daily diary with a list of the most likely possible adverse events (see **Table 10**), where they can document expected and other unexpected events not already listed. All non-serious adverse events will be reported to the IRB during continuing review. All AEs regardless of severity level will be evaluated by the DSMB during scheduled meetings.

If a participant reports an AE/SAE that does not yet have a Date of Resolution (ongoing) and is continuous (no more than two days without interruption) across two follow-up periods, this AE/SAE will be considered one event. The total duration of the AE/SAE will be collected but only one AE/SAE report form will be completed for this particular event. If the symptoms resolved for more than two days before recurrence, these will be reported as separate events.

The study staff will record all reportable events with start dates occurring any time after informed consent is obtained until 7 (for non-serious AEs) or 30 days (for SAEs) after the last day of study participation. At each study visit, the study staff will inquire about the occurrence of AE/SAEs since the last visit. Events will be followed for outcome information until satisfactory resolution or stabilization. In the event of SAEs, all clinical and laboratory investigations considered necessary by the investigator will continue until values have returned to normal. The investigator will provide the IRB with copies of results of examinations and treatment carried out during the follow-up of SAEs. These reports will be provided to the FDA and the NCCIH Program Official.

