7.3 Adverse Events and Serious Adverse Events

An **adverse event (AE)** is any untoward medical occurrence in a participant during participation in the clinical study or with use of the experimental agent being studied. An adverse finding can include a sign, symptom, abnormal assessment (laboratory test value, vital signs, electrocardiogram finding, etc.), or any combination of these regardless of relationship to participation in the study. This includes events not

present at the start of the study, or worsening in grade during the course of the study. An AE can be reported anytime after study enrollment; a participant is considered enrolled once the informed consent form is signed.

A serious adverse event (SAE) is one that meets one or more of the following criteria:

- Results in death
- Is life-threatening (places the participant at immediate risk of death from the event as it occurred)
- Results in inpatient hospitalization or prolongation of existing hospitalization
- Results in a persistent or significant disability or incapacity
- Results in a congenital anomaly or birth defect

An important medical event that may not result in death, be life threatening, or require hospitalization may be considered an SAE when, based upon appropriate medical judgment, the event may jeopardize the participant and may require medical or surgical intervention to prevent one of the outcomes listed in this definition.

Unanticipated Problems (UP): The Office for Human Research Protections (OHRP) considers unanticipated problems involving risks to participants or others to include, in general, any incident, experience, or outcome that meets **all** of the following criteria:

- Unexpected in terms of nature, severity, or frequency given (a) the research procedures that are described in the protocol related documents, such as the IRB-approved research protocol and informed consent document; and (b) the characteristics of the participant population being studied;
- Related or possibly related to participation in the research (“possibly related” means there is a reasonable possibility that the incident, experience, or outcome may have been caused by the procedures involved in the research); and
- Suggests that the research places participants or others at a greater risk of harm (including physical, psychological, economic, or social harm) than was previously known or recognized.

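### Addendum B explains an expected female excess of reported GI events by anatomy, but plans nothing to separate occurrence from readiness to report and makes no use of the pre-antibiotic information the trial collects

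*Combined protocol and SAP*

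**What the plan says.** Appendix 4 (Addendum B) hypothesises that females "would report more GI related adverse events since their biological anatomy tends to predispose them to increased GI discomfort". Its background offers two kinds of explanation. One is physiological: "Women have increased sensitivity throughout the whole digestive tract making them more vulnerable to GI pain, bloating, and nausea", with a longer colon and slower transit. The other is behavioural: a study of physician visits for constipation found that "females were more likely to report GI discomfort and seek medical assistance when ill".

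The plan is brief: "we propose analyzing the previously collected data on the adverse events reported by males and females", pooled over the R61 (YOBIOTIC) and R33 (OURBIOTIC) cohorts to raise the sample size, plus a comparison of short-chain fatty acid data by sex. No model, adjustment or baseline comparison is given.

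The parent protocol collects more than the addendum uses. Section 7.2 has the study staff "record all reportable events with start dates occurring any time after informed consent is obtained", and Section 7.3 agrees: "An AE can be reported anytime after study enrollment; a participant is considered enrolled once the informed consent form is signed". Section 4.5 puts consent about 45-60 days before the interventions. The daily diary, which carries the adverse-event checklist, covers days 1-14 only (Section 7.2; Table 8, footnote b). The GSRS-IBS is listed at the pre run-in baseline and on days 7 and 14 in the précis schedule, but on days 1, 7 and 14 in Table 8 as it reads here.

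Appendix 3 (Addendum A) hypothesises that "a higher intake of dietary fiber will result in participants experiencing fewer adverse events from the antibiotic", and it too names no pre-dose symptom comparison.

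**The concern.** The outcome is what participants choose to report. If females report GI discomfort more readily, as the addendum's background says, their counts will be higher even when the same events occur in both sexes. Every participant takes amoxicillin-clavulanate, so no unexposed group can show the background difference. A count taken during treatment contains no earlier value for the same person. Restricting adverse events to new or worsening ones (Section 7.3) does not correct for readiness to report them.

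Pooling the cohorts does not help. A reporting difference does not shrink as the sample grows, so a larger sample makes a false attribution more likely. At stake is the interpretation: a reporting difference could be published as an effect of female anatomy or, in Addendum A, a pre-existing link between fiber and symptoms as fewer antibiotic side effects.

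**Working it through.** Addendum B gives no sample size, effect size or alpha, so there is no figure to reproduce. The check asks how often reporting alone would give a significant female excess.

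**Inputs from the documents**
- Event rate: the GI terms in Table 1 (Section 2.10) total 41 in controls and 21 with BB-12. 41 + 21 = 62 events in 40 adults, and 62/40 = 1.55 each.
- Sex split: about 50% women (précis), so 30 per sex of 60.

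**Assumptions**
- Females report r = 1.2, 1.35 or 1.5 times as readily as males, with identical true events.
- Pooled size 120 (60 per sex); the R33 size is not in the documents.
- Counts are Poisson with gamma variation between people (shape 2), so the variance is μ + μ²/2.

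**Formulas.** Hold the overall mean at 1.55. Male mean m = 2 × 1.55/(1 + r); female mean f = r × m. With n per sex, the standard error of the log rate ratio is √[(1/m + 1/f + 1)/n]. The chance of a significant female excess is Φ(ln r/SE − 1.96).

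Example, r = 1.5 and n = 30: m = 1.24, f = 1.86. SE = √[(0.806 + 0.538 + 1)/30] = 0.280. ln 1.5 = 0.405, so 0.405/0.280 = 1.45. Φ(1.45 − 1.96) = 0.31.

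| r | m | f | SE, N=60 | Chance, N=60 | SE, N=120 | Chance, N=120 |
|---|---|---|---|---|---|---|
| 1.0 | 1.55 | 1.55 | 0.276 | 2.5% | 0.195 | 2.5% |
| 1.2 | 1.41 | 1.69 | 0.277 | 10% | 0.196 | 15% |
| 1.35 | 1.32 | 1.78 | 0.278 | 19% | 0.197 | 33% |
| 1.5 | 1.24 | 1.86 | 0.280 | 31% | 0.198 | 54% |

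Simulation of the same model with a quasi-Poisson test gives about 10%, 18% and 30% at N=60, and 14%, 33% and 53% at N=120.

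**Second model.** Compare the proportion of each sex with any reported GI event. Assume a true probability of 0.3 to 0.7 in both sexes, reported with probability 0.9 by females and 0.7, 0.6 or 0.5 by males. The observed ratios are 0.9/0.7 = 1.29, 0.9/0.6 = 1.50 and 0.9/0.5 = 1.80, although the true ratio is 1. A significant difference appears in 8% to 59% of studies at 30 per sex and 12% to 88% at 60 per sex.

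**Does a pre-dose reference remove the bias?** Take true rates of 1.0 before and 2.5 on treatment in both sexes, reported with probability 0.6 by males and 0.9 by females.
- Difference scale: males 0.6 × (2.5 − 1.0) = 0.90; females 0.9 × (2.5 − 1.0) = 1.35. A spurious sex difference remains.
- Ratio scale: males 1.50/0.60 = 2.5; females 2.25/0.90 = 2.5. The bias is gone, provided each person's readiness to report is the same in both periods.

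A change score therefore removes an additive reporting difference but only reduces a multiplicative one. At N=60 and r = 1.5, simulation of change in counts lowers the false excess from about 30% to about 7-21%. The higher end applies when the assumed pre-dose rate is a small share of the on-treatment rate.

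**The case against.** The strongest reply is that the hypothesis, read literally, is about reporting: it predicts that females will report more GI events, and a comparison of reported events tests that. It does not claim that females react more strongly to the antibiotic. Greater female GI sensitivity is the addendum's proposed explanation, not a nuisance to be removed. This stands. The weakness lies in the causal clause and in how an excess would be read, not in the comparison itself.

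A reader might infer that adverse events have no pre-antibiotic reference at all. The documents do not support that. Events are recorded from consent, through the run-in. The accurate statement is that Addendum B plans no use of them, and that they are not like for like, because the diary checklist starts on day 1.

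A reader might also infer that the comparison would probably confirm the hypothesis under identical reactions. Of the six scenarios with r above 1, only one exceeds one half (r = 1.5 at N=120), and it rests on two assumptions.

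The event rate comes from adults with respiratory infections on 10-day penicillin-class courses, and 12 of the 62 events are decreased appetite. Without those 12 the rate is 50/40 = 1.25. The same formula then gives 9%, 17% and 27% at N=60, and 14%, 30% and 49% at N=120, so the conclusion does not depend on that choice.

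Finally, the GSRS-IBS is self-reported too, and the R33 protocol is not among the documents. Both points stand and limit the remedy: the GSRS-IBS can support the event comparison but should not replace it.

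**Conclusion.** The concern holds in a limited form. Addendum B credits anatomy with an excess that its own background could also credit to reporting, and it plans no step to tell the two apart. Reporting alone could produce a significant female excess in about 10-30% of studies at N=60 and 14-53% at N=120, against a nominal 2.5%. These figures rest on assumed reporting ratios of 1.2-1.5, an assumed pooled size, and an event rate borrowed from a different population; they show that the risk is material, not how large it is in this trial. Addendum A shares the gap in its claim about events from the antibiotic. Both substudies are exploratory and no go/no-go role is stated for them, so this is a worthwhile, inexpensive improvement rather than a threat to the main trial.

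**What to change.** 1. Keep the comparison of reported GI adverse events by sex, but limit its conclusion to reported events. Do not attribute an excess to anatomy or to the antibiotic from event counts alone.
2. Add, as a supporting analysis, the female-male difference in GSRS-IBS change from the first assessment to days 7 and 14. Before doing so, reconcile the précis schedule (pre run-in) with Table 8 (day 1). Day 1 is also the antibiotic start, so establish whether that value is pre-dose. Confirm that the R33 cohort has the same data.
3. State that a change score removes additive but not multiplicative reporting differences. Add a ratio-scale sensitivity analysis, with its assumption of constant readiness to report.
4. Show the female:male rate ratio for non-GI events beside the GI ratio as a negative control.
5. In Addendum A, apply the same pre-dose GSRS-IBS reference before describing a fiber association as fewer events caused by the antibiotic.

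The cost is addendum wording and a little more analysis, using data the R61 trial already schedules. The drawback is that the negative control will be imprecise, because non-GI events are likely to be few in healthy adults.

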Enrollment		Post run-in health status	Diary start	Fecal sample	GSRS-IBS		
Demographics		Randomization		Follow-up	Fecal sample		
Baseline health					Follow-up		
GSRS-IBS							
Fecal sample							

Sample Size and Population:

The population will be generally healthy adults of ages 18-65 years. This randomized controlled trial is open to all eligible adults who meet the inclusion criteria. We are not proposing exclusion of any specific sex/gender or racial/ethnic group. One hundred participants will be recruited from the greater community and clinical sites in the Washington, DC metropolitan area, and sixty (n=60) participants will be randomized and commence the study. Based on the demographics of the network and recruitment rates in previous studies at our site, we anticipate about 50% of participants will be women, 20% will be Spanish speakers, and 30-40% will self-identify as one of the racial or ethnic minority populations.

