9.2 Sample Size and Randomization

Sample size calculations were informed by data from Hoverstad et al.,(120, 121) which compared changes in the mean SCFA levels between baseline fecal samples and fecal samples collected after six days administration of various antibiotics or placebo in healthy volunteers. In these studies, a mean reduction in acetate levels occurred from 45 ± 16 umol/g at baseline to 24 ± 18 umol/g after antibiotic treatment (46% reduction in acetate). Reductions in acetate after antibiotic treatment ranged from 5% to 79% with ampicillin, a similar antibiotic to amoxicillin.(120, 121) We can infer similar decreases in acetate in our proposed study. Using a conservative estimate of a 42% decrease in acetate in the control/antibiotic treated group and no greater than a 15% decrease in the BB-12 treated group, and an allocation ratio of 2:1 (BB-12 to control volunteers); a total sample size of 60 participants is necessary to have 80% power to detect a significant difference in mean acetate levels as a measure of gut microbiota production of SCFA between a control and BB-12-treated group.

With a sample size of 40 subjects in the active arm and 20 subjects in the control arm and attrition rate of 5% at day six and 20% at day 30, we would have power of 82% to detect a moderate effect size of Cohen's $d = 0.63$ (assuming the intra-correlation correlation coefficient is 0.3). The α level of 0.05 will be used for the analysis. Since the effect size of previous study (reduction in acetate levels) is Cohen's $d = 1.23$, we should have ample power to detect the treatment effect. (The power calculation is based on the R software and packages simr, sjstats, and pwr).

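### Substudy Addendum B reuses the OURBIOTIC data in which a female excess of adverse events was already seen, so a combined analysis with YOBIOTIC overstates the evidence in the hypothesised direction

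*Combined protocol and SAP*

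**What the plan says.** Appendix 4 first describes anatomical and physiological differences between the sexes. From these it hypothesises that "females in the parent studies (R61/YOBIOTIC and R33/OURBIOTIC phases) would report more GI related adverse events", giving as the reason "since their biological anatomy tends to predispose them to increased GI discomfort".

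The next paragraph reports what had already been seen: "We observed more incidences of adverse events reported by females compared to males in the current OURBIOTIC study". The proposal follows directly: "For this substudy, we propose analyzing the previously collected data on the adverse events reported by males and females". YOBIOTIC is brought in because the two studies are similar: "we propose studying both cohorts to increase the sample size".

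The addendum names no test, significance level, sidedness or model. It plans no analysis by cohort and does not label the comparison post hoc or exploratory. A second aim compares short-chain fatty acids between the sexes; no earlier look at those data by sex is described.

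**The concern.** When an analysis is prompted, even in part, by an excess seen in some of the data, those data are no longer neutral evidence on whether the excess is real. If the OURBIOTIC excess was chance, it enters the combined result at full weight, and YOBIOTIC can only dilute it. The p-value in the expected direction is then too small and the estimated difference too large.

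YOBIOTIC is a separate cohort that could show whether the excess recurs. As the addendum is written, it adds numbers and is given no role as a replication. A reader of the combined result could not tell how much of it comes from the cohort that had already been looked at.

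**Working it through.** The addendum gives no sample size, power or significance level, so there is no figure of its own to reproduce. The check asks how often a combined test would find more events in females when the sexes do not differ, given that OURBIOTIC has already shown an excess.

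**Inputs from the documents**
- YOBIOTIC size, from the Précis (Sample Size and Population): "sixty (n=60) participants will be randomized and commence the study".
- Sex split, same place: "we anticipate about 50% of participants will be women". That gives 60 × 0.5 = 30 women and 30 men.
- Significance level, from Section 9.2, stated for the main analysis only: the "level of 0.05 will be used for the analysis". It is borrowed here, giving 2.5% in each direction.

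**Assumptions, because the documents give no figure**
- w, the share of the total information held by the OURBIOTIC data already seen: 0.25 to 0.70.
- c, the z-value that the OURBIOTIC excess had to pass to be noticed: 0 (any excess) or 1 in the main range, with 0.5 and 1.645 for comparison.
- Gastrointestinal events and all adverse events behave alike.

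**Formula.** Let Z1 be the statistic from the OURBIOTIC data already seen and Z2 the statistic from the remaining data. They are independent standard normals when there is no difference. The combined statistic is Z = √w·Z1 + √(1−w)·Z2, and

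P(Z > 1.96 | Z1 > c) = ∫ from c to ∞ of φ(x)·[1 − Φ((1.96 − √w·x)/√(1−w))] dx ÷ [1 − Φ(c)].

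**Rejection rate in the female direction (nominal 2.5%)**

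| Excess noticed at | w = 0.25 | w = 0.30 | w = 0.50 | w = 0.70 |
|---|---|---|---|---|
| any (c = 0) | 4.5% | 4.7% | 4.9% | 5.0% |
| z > 0.5 | 6.3% | 6.6% | 7.6% | 8.1% |
| z > 1 | 9.1% | 9.9% | 12.8% | 14.9% |
| z > 1.645 | 14.7% | 16.7% | 25.1% | 34.4% |

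**Two-sided rate.** At c = 0 the two-sided 5% test keeps 5.0% at every w, by symmetry. Most of it has moved to one side: at w = 0.50 it splits into 4.94% for more events in females and 0.06% for fewer. At z > 1 the two-sided rate is 9.2% (w = 0.25) to 14.9% (w = 0.70).

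**Check on counts.** Simulation with 30 women and 30 men in each cohort and equal event rates of 0.3, 0.5 or 0.7 in both sexes:
- Any strict excess of women in OURBIOTIC: combined rejection in the female direction 5.8 to 6.0%, against 2.6 to 2.7% without selection. The mean pooled difference is 5.3 to 5.7 percentage points when the truth is zero.
- Excess of at least 10 points: two-sided rate 9.5 to 9.9%, mean pooled difference 7.7 to 8.1 points.
- Excess of at least 17 points (5 of 30): two-sided rate 16.5 to 17.9%, mean pooled difference 10.3 to 10.7 points.
- YOBIOTIC alone, after the same selections: 2.3 to 2.6% in the female direction and 4.7 to 5.3% two-sided, which is close to nominal.

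**Power of YOBIOTIC alone**, for event rates of 50% and 70% at two-sided 0.05:
- 30 per sex: SE under no difference = √(0.6 × 0.4 × 2/30) = 0.1265; SE under the alternative = √((0.25 + 0.21)/30) = 0.1238. Power = Φ((0.20 − 1.96 × 0.1265)/0.1238) = Φ(−0.387), about 35%.
- 60 per sex, if OURBIOTIC were also 60 people: the SEs are 0.0894 and 0.0876, and power is Φ(0.282), about 61%. That figure is nominal and ignores the selection.

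**The case against.** The strongest reply is that the hypothesis has its own basis. The addendum cites greater gut sensitivity, colon length, transit time and care-seeking, states the hypothesis, and only then mentions the observation. A reader might infer that the OURBIOTIC excess produced the hypothesis and that any pooled p-value is therefore invalid. The documents do not support that. They do not say which came first, no test is named to be called invalid, and a two-sided test keeps its overall 5% if only the direction was noticed. Nor do they say that a chance result would be presented as confirmed in two studies. What remains is narrower: an independent rationale does not make the OURBIOTIC data fresh evidence.

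Further points stand in part:
- The observation covers all adverse events and the hypothesis gastrointestinal ones. Carry-over could be weaker than calculated, although at least 8 of the 12 expected events in Table 10 are gastrointestinal.
- OURBIOTIC is described as current, so only part of it may have been seen. The lower end of the range for w allows for this.
- The protocol title calls the work exploratory and the addendum discloses the earlier look openly. Both soften the point. But Section 9.8 labels the main secondary analysis exploratory and Appendix 3 speaks of exploring existing data, while Appendix 4 carries no such label.
- Testing in YOBIOTIC alone would miss a difference of 50% versus 70% about two times in three. This is a good reason not to make it the only analysis.

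**Conclusion.** The point holds in a limited form. Appendix 4 includes the data in which the female excess was noticed and gives YOBIOTIC no separate role, so a combined analysis overstates the evidence for more events in females. Against a nominal 2.5% in that direction, the rate is about 4.5 to 5.0% if direction alone prompted the look and about 9 to 15% if the excess was at z>1. This rests on three assumptions: the OURBIOTIC data already seen hold 25 to 70% of the information, gastrointestinal and all adverse events behave alike, and there is no true difference. The actual figure cannot be fixed from the documents.

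The matter is minor. It concerns a secondary analysis of collected data. A reader might extend it to the sex comparison of short-chain fatty acids or to the trial's main result. Neither follows: no earlier look at the fatty acid data by sex is described, and the primary acetate outcome (Section 9.5.1) and the criterion for moving to the R33 phase (Section 9.1) do not use these data.

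**What to change.** Amend Appendix 4 as follows:
- Report the sex difference in gastrointestinal adverse events separately for each cohort, with intervals.
- State that OURBIOTIC is hypothesis-generating, and say how much of it had been seen and how large the excess was.
- Treat YOBIOTIC as the independent check, provided its adverse events have not already been examined by sex; the documents do not say, so the addendum should.
- Give the pooled estimate stratified by cohort, with its interval, labelled exploratory and with the earlier look noted beside it.

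The cost is addendum wording and a small amount of extra analysis; no new data are needed. The downside is imprecision: with about 30 women and 30 men, YOBIOTIC alone has about 35% power for 50% versus 70%. The addendum should therefore say that a null result there is not evidence of no difference.
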